
Hypothesis

Our hypothesis is that there will be a change in *optic nerve sheath diameter (ONSD) with the raised PCO₂ and internal jugular venous occlusion*

Objective of study

The main objective of this study is to determine the changes in ONSD with controlled increase in intracranial pressure with hypercapnia and jugular venous occlusion in healthy human volunteers.

Proposed Methodology

The study will be conducted in accordance with guidelines set forth by the University of Toronto, University Health Network Ethics Committee for use of human subjects in research. Ethics board approval will be obtained as well as written consent from each subject.

Study Design

This will be a prospective, non-randomized, observational study.

Recruitment

Healthy volunteers will be recruited by poster advertisement around the hospital. They will be asked to contact [name], Research coordinator for the study. His contact number and email will be provided. They will then be screened according to the inclusion and exclusion criteria's to see if they are suitable for the study.

Inclusion criteria

Adult healthy volunteers who are above the age of 18

ASA 1

Body mass index (BMI) less than and equal to 35

Neurologically normal subjects with no symptoms other than occasional non-severe headache

Exclusion criteria

BMI above 35

Lack of informed consent

Language barrier

Medical students and/or anesthesia residents going through the department as part of their rotation

Pregnancy

Frequent migraine headache

Informed Consent

The background of the study, benefits and risks will be explained to the subject and the informed consent form will be signed and witnessed if the subject agrees to participate.

Study protocol

Ultrasound measurement of ONSD

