All volunteers will be fully awake throughout the study and be kept comfortable. The transocular ultrasound examinations of the ONSD will be carried out using a SonoSite Edge (FUJI FILM SonoSite Inc. US) ultrasound system and a 7-10 MHz linear probe. Two trained investigators will perform investigations on both eyes of all subjects independently without being aware of each other's study results. All patients will be in the supine position and the probe will be gently placed on the temporal part of the closed upper eyelid. Contact with the eye will be gentle at all times and pressure never directly applied on the globe with the probe. A Tegaderm film (Transparent film dressing, 3M Canada) will be applied over the eye to protect the patient from the ultrasound gel applied during sonography. Once the anterior part of the optic nerve is depicted in the transverse/axial plane showing the papilla and optic nerve in its longitudinal course, the ONSD will be assessed 3 mm behind the papilla, as described previously (Figure 3). Each eye will be examined 3 times by each investigator and the mean value of the ONSD will be used for further calculations.

Carbon dioxide Manipulation

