A custom made collar consisting of two (2 x 3 x 1.5 cm) soft gauze pledgets held over the IJV by an elastic retainer will be applied around the patient's neck which can be adjusted to the subject's neck circumference using Velcro.(Velcro, US) This will apply only minimal pressure on the neck, which is comparable to wearing a tight dress shirt. In order to confirm the jugular venous occlusion with the neck collar, we will measure the diameter and flow in the IJV using the ultrasound in each subject in both sitting and supine positions with and without collar. Similarly to determine the lowest pressure needed to occlude the IJV, a 100 ml fluid (normal saline) bag which is attached to a pressure manometer will be placed on the subjects' neck below the collar and the minimal pressure at which there is complete occlusion of IJV will be recorded. The venous compression neck collar will be applied at each CO₂ levels (normocapnia, Hypercapnia I and II and hypocapnia) and ONSD measurements will be measures before and after the collar.

Risks

1. Carbon dioxide

The physiologic stresses of CO₂ manipulation on this proposal can be considered minimal. The higher PetCO₂ required will not exceed 60 mmHg nor will this change be sustained for long (10 minute intervals). The lower level of PetCO₂ is frequently seen with exercise. This range of PetCO₂ is physiological and is experienced repeatedly by most people over a regular day. Hyperventilation with hypocapnic PetCO₂ is common in day-to-day living (anger, excitement, running). Taking sedatives (alcohol) or even normal sleep can be associated with a PCO₂ of ~ 50 mmHg.

2. RespirAct™

The inhaled gases used in this study are supplied by a computerized MPET system. During control conditions, room air will be supplied at flow greater than the subject's minute ventilation. The subject will be monitored continuously for heart rate, depth of sedation and saturation by pulse oximetry by an attending physician (neurosurgery/ICU or anesthesia). When there is any concern about the subject's condition an alarm button on the RespirAct™ will deliver 100% oxygen to the subject as an extra safety feature. The re-breathing circuit can be easily removed from the subject's face.

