The physiological effect jugular venous compressions used in this study are minimal and the brief period of jugular occlusion is similar to the effects produced

by straining, coughing and heavy lifting. Neck collar will apply only minimal pressure on the neck, which is comparable to wearing a tight dress shirt and a tie.

4. Ultrasound

There are no risks with the use of ultrasound. Orbital ultrasound is routinely done in all patients coming for cataract and retinal surgery at Toronto Western Hospital. Around 30 patients undergo transorbital ultrasound every day at UHN. Ultrasound Gel can be cold on contact with skin.

Data collection

Data collected will include:

- Volunteer demographics
- Medical history
- Vital signs- Heart rate, non-invasive blood pressure and cardiac output, oxygen saturation, end-tidal Co₂ levels.
- Optic nerve sheath diameter at normocapnia, 2 levels of hypercapnia and hypocapnia.
- Internal jugular vein diameter and flow in supine and Siting position with and without the neck collar.
- The minimal pressure needed to occlude the IJV.

Data Analysis

A paired t test will be used to compare the following changes in ONSD

- Normocapnia (baseline Pco₂) to hypercapnia (baseline+10 mmHg)
- Normocapnia (baseline Pco₂) to Hypercapnia (baseline+15mmHg)
- Normocapnia (baseline Pco₂) to hypocapnia (baseline -10mmHg)
- Neck collar ON and OFF at each Co₂ levels.

Sample size

Since this is a preliminary study to evaluate the effect of hypercapnia and hypocapnia and IJ compression on ONSD, only a small sample is required. We intend to enroll 15 subjects in this initial phase. Given the fact that the CO₂ manipulation technique using the RespirAct™ is a new method developed at the University of Toronto and not yet widely available, the lack of information in the literature regarding its utilization for this purpose is obvious. We believe that this small sample will be sufficient to demonstrate the feasibility of the test and set the stage for larger studies.

Project Feasibility

We anticipate no difficulty in obtaining 15 volunteers to participate in this study. The RespirAct™ gas blender used for CO₂ manipulation has been installed at 10 sites including John's Hopkins, University of Colorado, Duke University, University of Nottingham, University of Montreal, University of Texas, and McGill University. The device has a proven track record with regard to clinical implementation.

Figures

[figure not shown]

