Figure 1: Experimental protocol demonstrating target PetCO₂ levels with measurements being performed both while the venous compression collar is off and then subsequently applied.

[figure not shown]

Figure 2: An experiment of end-tidal CO₂ (PetCO₂) manipulation using MPET (RespirAct™). Please note the stable O₂ levels and the precision control of PetCO₂ levels.

[figure not shown]

Figure 3: Two-dimensional ocular sonography. A diagram showing the ultrasound probe, the ocular globe and the optic nerve with the optic nerve sheath diameter (ONSD) which was measured 3 mm behind the papilla using an electronic caliper (A X LONG measure) and an axis perpendicular to the optic nerve (B + LONG measure).

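### The collar is tested only level by level: four separate paired t tests and no overall estimate, although jugular occlusion is half of the hypothesis

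*Combined protocol and SAP*

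**What the plan says.** The Data Analysis section states: "A paired t test will be used to compare the following changes in ONSD". Three items follow for CO2: normocapnia against baseline +10, +15 and −10 mmHg. The fourth item is the collar: "Neck collar ON and OFF at each" CO2 level. The neck collar section fixes how many levels that means: "levels (normocapnia, Hypercapnia I and II and hypocapnia) and ONSD measurements will be measures before and after the collar". The Figure 1 caption agrees, with "measurements being performed both while the venous compression collar is off and then subsequently applied". The plan therefore holds 3 + 4 = 7 paired tests.

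The hypothesis is a change in ONSD with raised PCO2 "and internal jugular venous occlusion". The main objective is to "determine the changes in ONSD with controlled increase in intracranial pressure with hypercapnia and jugular venous occlusion". The Sample size section gives 15 subjects and adds hypocapnia to the conditions being evaluated. It calls the study preliminary and expects the sample to be "sufficient to demonstrate the feasibility of the test and set the stage for larger studies".

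The plan states no significance level, primary comparison, multiplicity rule or pooled collar analysis.

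**The concern.** Half of the hypothesis asks one question: does jugular occlusion change ONSD? The plan answers it with four p-values and no rule for combining them. Two misreadings follow.

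- If the collar works equally at every CO2 level, limited power at n = 15 will often make it significant at some levels and not at others. That pattern looks like a collar effect that depends on CO2, even when there is none.
- If the collar does nothing, there are four chances for an isolated significant result.

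Either could mislead the larger studies that this one is meant to prepare. The design can answer the overall question directly, because every subject is measured with the collar off and on at all four levels. The plan just does not use the data that way.

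**Working it through.** **Inputs from the plan.** n = 15; four CO2 levels; collar off and on at each; paired t tests (14 df). The plan gives no error rate, effect size or SD, so it has no figure of its own to reproduce.

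**Assumptions (not in the plan).** Two-sided 0.05 per test; normal data; CO2 contrasts taken with the collar off; one ONSD value per subject and condition. The last is a reading of "Each eye will be examined 3 times by each investigator and the mean value of the ONSD will be used for further calculations". Effects are in SDs of the paired on-minus-off difference, and r is the correlation between a subject's four such differences. The plan gives no r, so a range is shown.

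**1. Same collar effect at all four levels: how often are the results mixed?** Mixed means at least one test significant and at least one not.

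For an effect of 0.5 SD, the noncentral t power of one test is p = 0.438. With r = 0:

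P(mixed) = 1 − p⁴ − (1 − p)⁴ = 1 − 0.0368 − 0.0998 = 0.863.

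Simulation gives the other cells:

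| Effect (SD) | r = 0 | r = 0.3 | r = 0.5 | r = 0.75 |
|---|---|---|---|---|
| 0.25 | 47% | 41% | 35% | 25% |
| 0.5 | 86% | 73% | 61% | 43% |
| 0.75 | 64% | 54% | 46% | 33% |
| 1.0 | 19% | 17% | 15% | 11% |

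**2. No collar effect: chance that at least one of the four collar tests is significant.** With r = 0 this is 1 − 0.95⁴ = 0.185.

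Correlation lowers it. If subjects truly differ in collar response with SD s, in units of the error SD of one measurement, each difference has variance s² + 2, so r = s²/(s² + 2):

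- s = 1, r = 0.33: about 17%
- s = 2, r = 0.67: about 14%
- s = 5, r = 25/27 = 0.93: about 9%
- s = 10, r = 100/102 = 0.98: about 7%

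A CO2 effect that is the same with the collar off and on cancels from the on-minus-off difference. These rates therefore hold whether or not CO2 changes ONSD.

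**3. Neither CO2 nor collar has an effect: at least one of all seven tests significant.** Independence would give 1 − 0.95⁷ = 0.302. The CO2 contrasts share the normocapnia reading, so the tests are not independent. Simulation with independent measurement errors gives 26% to 27%. Over the covariance structures examined the range is 16% to 29%. If differences between subjects dominate, it falls further: 13% when the between-subject SDs of collar effect and CO2 slope are 10 times the error SD, with a limit of 1 − 0.95² = 9.75%.

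**4. What an overall collar estimate gives.** For one level the 95% CI half-width is 2.145/√15 = 0.55 SD. The SD of a subject's four-level mean is √((1 + 3r)/4), which multiplies that half-width:

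| r | Factor | Half-width (SD) | Power at 0.5 SD, two-sided 0.05 |
|---|---|---|---|
| 0 | 0.500 | 0.28 | 95% |
| 0.3 | 0.689 | 0.38 | 74% |
| 0.5 | 0.791 | 0.44 | 63% |
| 0.75 | 0.901 | 0.50 | 52% |

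One single-level test has 44% power at the same effect. For an equal effect at every level and the same alpha, the averaged test is more powerful for any r below 1.

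**The case against.** **The study is preliminary.** It aims at feasibility in healthy volunteers, and no decision hangs on a p-value. This stands. It lowers the weight of the point and makes formal multiplicity control optional. It does not supply an overall collar estimate, which a pilot needs as much as a confirmatory trial does.

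**The mixed-pattern figures describe low power, and the harm needs a misreading.** This is also fair. The plan nowhere says that it will infer a CO2-dependent collar effect, and the effect sizes and correlations are assumed. But four separate tests with no overall result invite that misreading, and the remedy is one line.

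**Averaging is not always better.** If alpha were split and the overall test run at 0.025, it would beat one unadjusted single-level test (at 0.5 SD) only when r is below about 0.62. That limits alpha splitting. It does not affect an overall estimate with a 95% CI.

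**Stronger readings that the documents do not support.**

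- A reader might infer that the study has one definable false-positive rate. It does not: the rate depends on an unstated decision rule and on which effects are real. Requiring both a hypercapnia test and a collar test looks strict, at about 3.5% or less, but only if neither factor has any effect. If CO2 works and the collar does not, that rule still credits the collar in up to about 18.5% of studies.
- A reader might infer that the hypocapnia test lies outside the study's purpose, since the hypothesis and main objective omit it. The Sample size section names it as part of that purpose.

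**Conclusion.** The point holds as a gap in the analysis of the collar. The plan offers four level-specific tests and no overall estimate for half of its hypothesis, although the design provides one at no extra measurement.

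Under the stated assumptions, an identical 0.5 SD effect at all levels gives a mixed pattern in about 86% (r = 0) to 43% (r = 0.75) of studies. With no collar effect, an isolated significant collar result arises in about 9% to 18.5%, whether or not CO2 acts. With no effect of either factor, about 16% to 29% of studies have at least one significant result among the seven. The last two ranges fall lower still if between-subject variation dominates.

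The documents do not support the conclusion that the study is invalid or that it must have family-wise error control. The importance is minor to moderate, and the change should be made because it costs almost nothing.

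**What to change.** In the Data Analysis section:

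1. Add one overall collar analysis: for each subject, the mean of the four on-minus-off ONSD differences, tested with a one-sample t test and reported with its 95% CI.
2. Keep the seven pairwise contrasts, label them exploratory, and report each as an estimate with a 95% CI.
3. State that a difference in significance between CO2 levels will not be read as a difference in collar effect.
4. State the significance level. Holm control over a named collar test and a named raised-PCO2 test is an option, not a requirement, in this preliminary study.

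This changes wording only and needs no new subjects, measurements or procedures. The one drawback is that an average can hide true differences between levels, which is why the level-specific contrasts stay.
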